#### **Effectiveness:**

The primary effectiveness endpoint is the responder rate at Month 6. A responder is defined as a subject who shows at least a 1-point improvement on the ALJDS from baseline based on EI assessment on both sides of the jaw. Baseline is defined as the last assessment by EI prior to randomization.

One-sided Fisher's exact test with 2.5% significance level will be used to compare responder rates between the treatment and control groups. If the 1-sided p-value is < 0.025 and the responder rate for the treatment group is statistically greater than 50%, then the primary effectiveness endpoint will be considered met. The primary effectiveness analysis will be performed on the intent-to-treat (ITT) population, which includes all randomized subjects.

Secondary effectiveness endpoints include EI and subject assessed GAIS responder rates, where a "responder" is a subject who shows improvement in the overall aesthetic assessment in jawline area (Improved or Much Improved on GAIS) at the Month 6 Visit, and subject mean overall satisfaction on the validated FACE-Q Satisfaction with Lower Face questionnaire at Month 6.

Secondary efficacy analyses will include:

- Responder rates with 95% CI for the treatment group based separately on the EI and subject assessments of GAIS, where a "responder" is a subject who shows improvement in the overall aesthetic assessment in jawline area (Improved or Much Improved on GAIS) at the Month 6 visit.
- Descriptive summary of the change in overall score of subject's satisfaction with lower face and jawline since baseline at the Month 6 visit based on the treatment group subjects' responses on the validated FACE-Q Satisfaction with Lower Face and Jawline questionnaire; a 2-sided paired t-test at the 5% level to demonstrate that the mean overall satisfaction score at Month 6 is statistically greater than that at baseline. This test is only performed if the primary endpoint is met.

No multiplicity adjustment will be made for the 2 GAIS responder rates, since these endpoints are descriptive in nature.

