# 3.2 Clinical Hypotheses

The responder rate at Month 6 in the treatment group will be statistically significantly greater than in the control group at Month 6, and the responder rate at Month 6 for the treatment group will be statistically significantly greater than or equal to 50%. Responder rate is the percentage of subjects who show at least 1-point improvement on the Allergan Loss of Jawline Definition Scale (ALJDS) from baseline based on both sides of the jaw.

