# 8.3 Hypothesis and Methods of Analysis

# 8.3.1 Primary Effectiveness Analyses

The study device will be determined to be clinically effective if at least 50% of subjects in the treatment group are observed to be responders (subjects who show  $\geq$  1-point improvement on the ALJDS compared with pretreatment) at Month 6 and if the responder rate for treatment group is statistically superior to the responder rate for the control group at Month 6. The following hypotheses will be tested:

$$H_o$$
:  $P_v < 50\%$   
 $H_a$ :  $P_v \ge 50\%$ 

and

$$H_o$$
:  $P_v \notin P_c$   
 $H_a$ :  $P_v > P_c$ 

where  $P_v$  and  $P_c$  denote the responder rates for the treatment group at Month 6 after last treatment and control group at Month 6 after randomization, respectively. The first

hypothesis will be tested using 2-sided 95% CI. The null hypothesis will be rejected if the lower bound of the 95% CI is greater than or equal to 50%. The second hypothesis will be tested using 1-sided Fisher's exact test at 2.5% significance level (or 2-sided Fisher's exact test at 5% significance level) to compare responder rates between the treatment and control groups. The null hypothesis will be rejected if the 1-sided p-value is < 0.025 (or 2-sided p-value is < 0.05).

The primary effectiveness analysis will be performed on the ITT population using the last observation carried forward for any missing assessment of the primary endpoint at the Month 6 Visit. Additionally, as part of sensitivity analysis, the primary effectiveness analysis will be repeated on the ITT population using observed data as well as using multiple imputation procedure. Details of the multiple imputation procedure will be provided in the statistical analysis plan. Furthermore, additional sensitivity analyses of the primary effectiveness endpoint will be performed on the ITT population, excluding subjects who were inadvertently unblinded to the EI or who did not have a baseline ALJDS score of 2 or 3.

The impact of investigational sites on the primary effectiveness analysis at Month 6 will be evaluated by presenting the primary effectiveness analysis by each site.

[figure not shown]

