The primary effectiveness variable is restoration of jawline definition based on the ALJDS evaluated by EIs. The primary effectiveness endpoint is the proportion of ALJDS responders at Month 6. A responder is defined as a participant who shows at least a 1-point improvement from baseline (pretreatment) on the ALJDS on both sides of the jaw.

Month 6 refers to 6 months after the last treatment (initial or touch-up) for participants in the treatment group and 6 months after randomization for participants in the control group.

The study device will be determined to be clinically effective if at least 50% of participants in the treatment group are observed to be responders on ALJDS at Month 6 and if the responder rate for the treatment group is statistically superior to the responder rater for the control group at Month 6. The following hypotheses will be tested:

$$H_0: P_v < 50\%$$

$$H_a: P_v \geq 50\%$$

and

$$H_0: P_v \leq P_c$$

$$H_a: P_v > P_c$$

where P_v and P_c denote the responder rates for the treatment group at Month 6 after the last treatment (initial or touch-up) and for the control group at Month 6 after randomization, respectively.

The primary effectiveness analysis will be performed based the mITT population using multiple imputation as described in Section 5.3.2. Missing values will be imputed using multiple imputation method. The pooled responder rates and 2-sided 95% CI for the responder rates in the treatment group and in the control group respectively, the pooled between-group difference in the responder rate and the corresponding 2-sided p-value will be calculated, by pooling the results from the 30 imputed data sets using PROC MIANALYZE with normal approximation in SAS.

The first hypothesis will be tested using the pooled 2-sided 95% CI for the responder rate in the treatment group. The null hypothesis will be rejected if the lower bound of the 95% CI is greater than or equal to 50%.

The second hypothesis will be tested using the pooled between-group difference in the responder rate and the corresponding p-value for the between-group difference. The null hypothesis will be

CONFIDENTIAL

Statistical Analysis Plan V25L-002

JUVÉDERM VOLUX™ XC

rejected if the 2-sided p-value is < 0.05 and the responder rate is greater for the treatment group than the control group.

In addition, the 95% CI on the proportion of responders based on the pooled estimate from the 30 imputed data sets will be provided for each treatment group.

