5.3.2. Main Analytical Approach

Two hypotheses regarding the proportion of ALJDS responders at Month 6 based on EI's assessment will be tested.

$$1) H_0: P_v < 50\%$$

$$H_a: P_v \geq 50\%$$

$$2) H_0: P_v \leq P_c$$

$$H_a: P_v > P_c$$

P_v denotes the responder rate for the treatment group at Month 6 after the preceding treatment and P_c denotes the responder rate for the control group at Month 6 after randomization.

The 2 hypotheses will be tested using the multiple imputation method as follows:

Step 1: The missing data will be imputed by each side of the jaw and treatment group using the fully conditional specification method with seed = 3575309 and nimpute = 30 based on the following model:

$$\text{Month 6 ALJDS} = \beta_0 + \beta_1 \text{Baseline ALJDS} + \beta_2 \text{Month 1 ALJDS} + \beta_3 \text{Month 3 ALJDS}$$

Step 2: After imputation, the changes from baseline will be calculated, from which the responder status in ALJDS at Month 6 of CP will be determined.

Step 3: Each complete dataset obtained from Steps 1 and 2 will be analyzed using SAS procedure FREQ

Step 4: The pooled results will be obtained using PROC MIANALYZE using normal approximation

The number and proportion of participants who achieved at least 1-point improvement from baseline at Month 6 during CP will be tabulated by treatment group. The pooled responder rates by treatment group and the associated p-value and 95% CI estimates based on the normal approximation will be presented. For the first hypothesis, the null hypothesis will be rejected if the lower bound of the 95% CI on the responder rate at Month 6 for VOLUX is greater than or equal to 50%. For the second hypothesis, if the 2-sided p-value is less than 0.05, then the ALJDS responder rate at Month 6 in JUVÉDERM VOLUX XC is statistically significantly different

[figure not shown]
CONFIDENTIAL

[figure not shown]
JUVÉDERM VOLUX™ XC

Statistical Analysis Plan V25L-002

from that in the no-treatment control group during the control period. Furthermore, if the responder rate is greater for JUVÉDERM VOLUX XC than the no-treatment control group, then VOLUX will be considered superior to the no-treatment control group.

The detailed SAS codes are as follows:

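### The sentence that defines clinical effectiveness asks only for an observed responder rate of 50%, while the formal test beside it requires the lower 95% confidence limit to reach 50%

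*SAP*

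**What the plan says.** Two statements of the 50% criterion stand in the same section of each document.

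- **The effectiveness sentence.** SAP Section 2 makes the conclusion of clinical effectiveness depend on two conditions: "if at least 50% of participants in the treatment group are observed to be responders on ALJDS at Month 6", and that "the responder rate for the treatment group is statistically superior to the responder rater for the control group at Month 6". Protocol Section 8.3.1 has the same pair, with the first condition worded "if at least 50% of subjects in the treatment group are observed to be responders".
- **The formal test.** SAP Section 2 then says of the first hypothesis: "The null hypothesis will be rejected if the lower bound of the 95% CI is greater than or equal to 50" percent. Protocol Section 8.3.1 has the same rule. The SAP interval is pooled over 30 imputed data sets, "using PROC MIANALYZE with normal approximation in SAS".

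Three other places give only the inferential form:

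- Protocol synopsis, Effectiveness: "the responder rate for the treatment group is statistically greater than 50" percent, as one of two conditions for the primary endpoint to be considered met.
- Protocol Section 3.2: the treatment-group rate "will be statistically significantly greater than or equal to 50" percent.
- SAP Section 5.3.2: rejection if the "lower bound of the 95% CI on the responder rate at Month 6 for VOLUX is greater than or equal to 50" percent.

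The SAP's list of changes to the protocol-planned analyses (Section 6.2.1) does not mention the point.

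**The concern.** An observed rate of at least 50% is a condition on the point estimate. A lower limit of at least 50% is a condition on the estimate minus its sampling error. The effectiveness sentence draws that contrast itself: responders are to be observed for the 50% bar, but superiority to control is to be statistical. It is also the only sentence in SAP Section 2 that leads to the words clinically effective; the confidence-limit sentence speaks only of rejecting a null hypothesis.

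If the result falls between the two thresholds and VOLUX beats control, someone quoting the effectiveness sentence can claim success on a result that fails the prespecified test. This is one of two required criteria in a study that the protocol labels pivotal. It also controls the FACE-Q paired t-test, which is run only if the primary criteria are met (protocol Section 8.3.2, SAP Section 5.4.2).

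**Working it through.** **Inputs.** From SAP Section 3 and protocol Section 8.5: 120 treated and 40 control participants for the power statement; 144 to 162 and 48 to 54 randomized; assumed responder rates of 80% and 40%. The test method, a normal approximation, is from SAP Sections 2 and 5.3.2. Complete data are assumed unless stated.

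**Reproducing the plan's figure.** Exact enumeration of the 1-sided Fisher test at 2.5%, with 120 and 40 participants and rates of 80% and 40%, gives 99.4% power. The stated value of more than 99% is confirmed.

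**The two thresholds.** With x responders of n and p = x/n, the observed rule is p ≥ 0.50. The test requires p − 1.96·√(p(1−p)/n) ≥ 0.50. At n = 144:

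- x = 83: 0.5764 − 1.96 × 0.0412 = 0.496, fails.
- x = 84: 0.5833 − 1.96 × 0.0411 = 0.503, passes.

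| n | Observed rule needs | Test needs | Rules disagree for |
|---|---|---|---|
| 120 | 60 (50.0%) | 71 (59.2%) | 60–70 (50.0–58.3%) |
| 144 | 72 (50.0%) | 84 (58.3%) | 72–83 (50.0–57.6%) |
| 162 | 81 (50.0%) | 94 (58.0%) | 81–93 (50.0–57.4%) |

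A Clopper-Pearson limit moves the top of the band only to 59.2%, 58.3% and 57.4%. The documents give no figure for the information lost to imputation. If 5% to 15% is assumed, the continuous threshold at n = 144 rises from 58.1% to between 58.3% and 58.7%.

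**The superiority condition.** Both rules also require VOLUX to beat control. With 144 and 48 participants, z = (p_v − p_c)/√(p_v(1−p_v)/144 + p_c(1−p_c)/48) must exceed 1.96.

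- At 72/144, control may be at most 16/48 (33%): 0.1667/0.0798 = 2.09. At 17/48, z = 1.81.
- At 83/144, control may be at most 19/48 (40%): 0.1806/0.0817 = 2.21. At 20/48, z = 1.94.

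Fisher's test gives nearly the same ceilings, 15/48 and 19/48.

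**Pass probabilities at 144 and 48.** On the 50% criterion alone, these are P(X ≥ 72) and P(X ≥ 84) for X binomial(144, p_v). The joint values sum the product of the two binomial probabilities over all (x, y) that meet the 50% rule and have z > 1.96.

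| True VOLUX rate | Control rate | Observed rule | Confidence-limit rule |
|---|---|---|---|
| 50% | criterion alone | 53% | 2.7% |
| 50% | 20% | 53% | 2.7% |
| 50% | 30% | 45% | 2.7% |
| 50% | 40% | 19% | 1.9% |
| 55% | criterion alone | 90% | 24% |
| 55% | 40% | 44% | 17% |
| 80% | 40% | 99.9% | 99.9% |

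**The case against.** The strongest reply is that the plan already shows which rule governs. The synopsis states when the primary endpoint is considered met, in inferential terms. Protocol Section 3.2 agrees, and SAP Section 5.3.2, the operative analysis section, carries only the lower-limit rule. In both sections that contain it, the observed-rate sentence introduces hypotheses that are then tested by the confidence limit. On this view it is a loose lead-in with no test attached.

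That stands as to intent. It does not remove the conflict: the lead-in states a condition for a conclusion, and that condition is not the one tested.

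Three stronger readings are tempting, and the documents do not support them:

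- **That any VOLUX rate of 50% to 58% both passes and fails.** The effectiveness sentence also requires superiority. At the planning ceiling of 40% control response, nearly all of the band fails on that condition under either reading.
- **That the chance of overall false success is about one half.** The 53% is for the 50% criterion alone. The joint probability reaches it only when control response is about 20%. At 40% control it is 19%.
- **That the synopsis adds a third threshold.** Its wording is the confidence-limit rule in words. The two could differ only if the lower limit were exactly 50%.

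**Conclusion.** The conflict is real and confined to one sentence, which appears in SAP Section 2 and in protocol Section 8.3.1. It bites when the observed VOLUX rate lies between 50.0% and about 57% to 58% and VOLUX also beats control, which at 144 and 48 participants needs a control rate of at most about 33% to 40%. There the literal sentence declares effectiveness and the formal test does not.

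How often this could happen depends on the true control rate, which the plan assumes only to be at most 40%. These figures rest on the normal approximation and complete data. Sample size and power are unaffected, because at the planned rates the rules give the same answer. The formal test itself is sound, and the correction is worth making because the conclusion sentence should match it.

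**What to change.** In SAP Section 2 and protocol Section 8.3.1, replace the observed-rate condition with: the lower limit of the 2-sided 95% CI for the treatment-group responder rate at Month 6 is at least 50%. Keep the superiority condition as it is. The synopsis, protocol Section 3.2 and SAP Section 5.3.2 already agree and need no change.

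The cost is one sentence in each document. No new data, analysis or sample-size change is needed. The edit makes the literal bar stricter, so it cannot be read as favouring the device.

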3. Sample Size Determination

Sample size is determined to provide adequate power to demonstrate that the product is effective as well as safe. A sample size of 120 participants in the treatment group and 40 participants in the control group will provide > 99% power to detect a difference of at least 40% in the responder rates between the 2 groups. This calculation is based on a 1-sided Fisher's exact test at the 2.5% level. The treatment group is assumed to have at least an 80% responder rate and the control group is assumed to have at most a 40% responder rate. Assuming a screen fail rate of 25% and a drop-out rate of 15% between randomization and the Month 6 visit, up to 280 participants will be enrolled, with at least 144 participants and at most 162 participants randomized to the treatment group and at least 48 participants and at most 54 participants randomized to the control group (3:1 ratio).

This sample size is considered adequate to determine the safety profile of the product in the jawline area. Assuming a screen fail rate of 25%, a 5% drop-out rate between randomization and initial treatment for the treatment group, and a 15% drop-out rate between randomization and optional treatment for the control group, it is estimated that at least 176 subjects will be treated in the study. With 176 treated subjects, there is at least 92% power to detect an AE related to treatment with an incidence rate of 1.5% in the population using a 1-sided exact binomial test at the 2.5% level.

The commercial software, PASS (2008, Version 8.0.13), was used for the power calculation. The sample size calculation used an inequality test for 2 proportions to demonstrate that the treatment group is superior to the control group. The safety calculation used an inequality test for 1 proportion.

4. Populations for Analysis

The 5 analysis populations will consist of participants as defined in [Table 4-1](#).

Table 4-1 Analysis Populations

Population	Definition	Study Treatment Assignment
mITT	All randomized participants with non-missing baseline on the ALJDS scale on both sides of the jaw	As randomized
Observed Primary Endpoint	All mITT participants who have Month 6 assessment on the ALJDS scale on both sides of the jaw	As randomized
Safety	All randomized participants who receive study treatment (VOLUX or control)	As treated ^a

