- ! For applicable effectiveness and safety endpoints, baseline is defined as the last non-missing value on or before the latter of randomization date or first treatment date in the control period, unless otherwise specified.
- ! Descriptive statistics for continuous variables include the sample size (N), number of non-missing observations (n), mean, standard deviation, median, 1st and 3rd quartiles, minimum, and maximum. For continuous data, a 2-sample t-test or Wilcoxon rank test will be used for between group comparisons as appropriate, unless stated otherwise. Specified that 95% CI for continuous variables will be based on the standard normal distribution in Section 5.1.
- ! Summary statistics for categorical variables include the sample size (N1), frequency count, and percentage. Ordinal categorical variables will be analyzed using the Cochran-Mantel-Haenszel test. Nominal variables will be analyzed using Pearson's chi-squared test or Fisher's exact test as appropriate. The 95% CI will be computed using the exact binomial method.
- ! The level of significance used for all statistical tests will be 0.05, 2-sided, unless stated otherwise.
- ! The change from baseline values will be computed as the value for the post baseline visit minus the baseline value, unless otherwise indicated.
- ! In the event if any data collected was after exit, it will not be included in tables but will only be presented in the listings.
- ! All statistical analysis will be performed using SAS version 9.3 or higher.
- ! MedDRA 22.1 or newer will be used to code AEs and medical history.
- ! WHO Drug Dictionary 201703 or newer will be used to code medications.

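### The SAP pools raw responder rates with a normal approximation: the control-arm 95% interval under-covers, the rule conflicts with SAP 5.1, and the move away from Fisher's exact test is not listed as a change

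*SAP*

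**What the plan says.** Protocol 8.3.1 says that superiority over control (hypothesis 2) is "tested using 1-sided Fisher's exact test at 2.5% significance level", with a 2-sided test at 5% as the alternative. It tests the 50% criterion (hypothesis 1) with a 2-sided 95% interval whose method it does not name. The power statement in SAP section 3 still rests on the protocol's test: "This calculation is based on a 1-sided Fisher's exact test at the 2.5% level".

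The primary analysis in SAP sections 2 and 5.3.2 is different. On the imputed data, "Each complete dataset obtained from Steps 1 and 2 will be analyzed using SAS procedure FREQ", and the rates, intervals, difference and p-value are then obtained "by pooling the results from the 30 imputed data sets using PROC MIANALYZE with normal approximation in SAS". Hypothesis 2 is "rejected if the 2-sided p-value is < 0.05 and the responder rate is greater for the treatment group than the control group". Hypothesis 1 passes if the lower 95% bound for VOLUX is at least 50%. Both must pass for the device to be called effective.

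For categorical variables, SAP 5.1 gives a general rule with no exception: "The 95% CI will be computed using the exact binomial method". SAP 6.2.1 lists the moves to mITT, to multiple imputation and to a new baseline definition, but not the move from Fisher's exact test to a normal approximation. Fisher's exact test remains for this endpoint only as sensitivity analysis 1, on observed data.

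**The concern.** Allocation is 3:1, so the control arm is small (40 evaluable, 48 to 54 randomized), and its responder rate is planned to be at most 40%. A normal-approximation interval for a raw proportion is weakest at small n and low rates. The same holds for an unpooled test of the difference when the smaller arm has few responders.

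At stake are the 95% interval reported for the control arm and the p-value reported for superiority. Two further matters are documentary: two interval rules apply to one primary proportion, and a change to the protocol's primary test is undeclared.

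**Working it through.** **Inputs.** Evaluable 120 v 40; randomized 144 v 48 to 162 v 54; rates 80% v 40%; drop-out 15% (SAP section 3). Decision rules as in SAP section 2. All figures are for complete data unless stated, by full enumeration of the two binomials.

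**The plan's own figure.** Power of the one-sided Fisher test at 2.5%, 120 v 40, 80% v 40%: 99.4%. This reproduces the stated > 99%. The unpooled normal test gives 99.6%.

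**Control-arm interval.** Wald: p̂ ± 1.96·√[p̂(1−p̂)/n]. For 5 responders of 48, p̂ = 0.104, SE = √(0.104 × 0.896/48) = 0.044, interval 1.8% to 19.1%. Wilson for the same data gives 4.5% to 22.2%. With no responders the Wald SE is 0 and the interval is a single point; at a true 2% rate and n = 48 the chance of that is 0.98^48 = 38%.

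Coverage at selected true rates:

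| n | Method | 2% | 5% | 10% | 20% | 30% | 40% |
|---|---|---|---|---|---|---|---|
| 40 | Wald | 55% | 87% | 91% | 91% | 93% | 95% |
| 48 | Wald | 62% | 91% | 86% | 93% | 93% | 92% |
| 54 | Wald | 66% | 93% | 91% | 92% | 94% | 93% |
| 48 | Wilson | 93% | 97% | 95% | 95% | 94% | 95% |

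Over rates of 5% to 40% in steps of 5 points, Wald covers 86-95% and Wilson 93-97% for n = 40, 48 and 54.

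**Hypothesis 2 alone.** Assumed unpooled form: z = (p̂v − p̂c)/√[p̂v(1−p̂v)/nv + p̂c(1−p̂c)/nc], reject if z > 1.96. One-sided size at a common true rate, against 2.5%:

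| nv/nc | Test | 5% | 10% | 20% | 40% | 50% | 60% | 70% | 80% | 90% |
|---|---|---|---|---|---|---|---|---|---|---|
| 120/40 | Unpooled | 11.5% | 5.9% | 4.3% | 3.2% | 2.9% | 2.4% | 2.2% | 1.7% | 1.3% |
| 144/48 | Unpooled | 9.2% | 5.5% | 4.3% | 3.1% | 2.8% | 2.4% | 2.2% | 1.8% | 1.3% |
| 162/54 | Unpooled | 8.1% | 5.0% | 3.9% | 3.1% | 2.8% | 2.6% | 2.2% | 1.9% | 1.2% |
| 144/48 | Fisher | 0.3% | 1.0% | 1.5% | 1.6% | 1.7% | 1.7% | 1.7% | 1.6% | 1.5% |

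Fisher's maximum over all rates is 1.6%, 1.7% and 1.9% at the three sizes.

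**Both hypotheses required.** Adding the 50% rule at 144/48, the joint error on equal rates is 0.0% up to 40%, 0.5% at 50%, 2.3% at 60%, 2.2% at 70% and 1.8% at 80%. The maximum is 2.3% (120/40), 2.4% (144/48) and 2.5% (162/54). After 15% drop-out from 144/48 (144 × 0.85 ≈ 122, 48 × 0.85 ≈ 41) it is 2.6%.

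**Hypothesis 1.** At n = 144 the Wald rule needs 84 responders: 0.5833 − 1.96·√(0.5833 × 0.4167/144) = 0.503, while 83 gives 0.496. The chance of 84 or more at a true 50% is 2.7%. The exact interval needs 85 (1.8%). At 120 the cut-offs are 71 and 72 (2.7% v 1.8%). At 162 both are 94 (2.5%).

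**Imputation.** A simulation at 144/48 assumed 15% missing completely at random, a simple binary imputation model (not the SAP's ALJDS model) and 30 imputations. It gave hypothesis 2 size of 3.2%, 4.2%, 5.5% and 8.3% at 40%, 20%, 10% and 5%, and control coverage of 87-94% over 5-40%. These are close to the complete-data figures.

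**Alternative tests.** At 144/48 the pooled-variance and Miettinen-Nurminen tests both have size 3.3% at a common rate of 90% and 3.6% at 96%. Hypothesis 1 is almost certain to pass there, so this is also the joint error.

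**The case against.** A reader might infer that the trial's false-positive rate is 4-9%. The documents do not support that. Those figures belong to hypothesis 2 alone at low common rates, where VOLUX could not clear 50%. Because both hypotheses must pass, the joint error there is essentially zero, and above a common rate of about 60% the unpooled test is conservative. This objection stands in full.

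A reader might also say that the SAP discarded the protocol's exact intervals. It did not: the protocol asks for a 95% interval without naming a method. The inconsistency is with SAP 5.1, and it can be read as a specific rule overriding a general one, since an exact binomial interval does not apply directly to a rate pooled over imputations. That is reasonable, but the SAP should say so.

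The unpooled variance is an inference. SAP 5.3.2 introduces SAS code that is not shown in the text available, so the form may be specified there. The hypothesis 2 sizes depend on it.

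Finally, Fisher's exact test survives as sensitivity analysis 1, the control-arm interval drives no decision, and at 80% v 40% Fisher and the unpooled test disagree with probability of only 0.16% (120/40) or 0.04% (144/48). All true. None of it makes the control-arm interval a 95% interval, or puts the test change in the list where a reader would look for it.

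**Conclusion.** The point holds for the reported intervals, for the nominal level of the hypothesis 2 p-value, and for documentation. It does not hold for the success decision.

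- The control-arm interval falls short of 95% over most of the planned range and fails badly near zero. This assumes a Wald interval on the raw rate, which is the natural reading of a normal approximation.
- The superiority p-value, read alone, is modestly optimistic at a common rate of 40% and more so at lower rates, provided the variance is unpooled.
- The overall decision stays close to its nominal 2.5%. The small excess at a true VOLUX rate of 50% comes from hypothesis 1 and discreteness, and disappears at 162. A Wilson or logit interval would not remove it: the cut-offs stay at 71 of 120 and 84 of 144. The one-responder difference from the exact rule is likewise absent at 162.

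The size and coverage figures are for complete data; the simulation that included missing data rests on an assumed mechanism and a simplified imputation model.

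**What to change.** 1. In SAP 2 and 5.3.2, compute each arm's 95% interval as a Wilson interval pooled over imputations. Pooling on the logit scale is an alternative, but is undefined for any imputed data set with no responders in an arm. State that this rule overrides the exact-binomial rule in 5.1 for the imputed primary endpoint.
2. State the variance form used for the between-group difference.
3. Add to 6.2.1 that hypothesis 2 moves from Fisher's exact test to a normal-approximation test on pooled results.
4. Keep Fisher's exact test, as in sensitivity analysis 1, as the named check on the hypothesis 2 p-value.
5. Do not adopt a pooled-variance or Miettinen-Nurminen test on the ground that it holds its level: with 3:1 allocation it raises error at high common rates, where hypothesis 1 gives no protection.

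The cost is a few lines of code, some SAP wording and slightly different reported intervals. Power stays above 99%.
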